1.1.2 Clinical studies

The tolerability and initial PK of AZD8931 was investigated in a phase I study (D0102C00001) in healthy male volunteers. D0102C00001 was the first administration of AZD8931 to humans and consisted of 2 parts. Part A was a randomised, double-blind, placebo-controlled, SAD design. Part B was a randomised, double-blind, placebo-controlled crossover design. Part A was designed to allow a gradual escalation of doses with intensive clinical monitoring to ensure the safety of the volunteers. In Part B, volunteers were dosed at the maximum tolerated dose (MTD). Volunteers were randomised to receive AZD8931 followed by placebo, or placebo followed by AZD8931, in a 2-period, randomised crossover design with a minimum of 7 days washout between treatments.

The results from Part A of the SAD study were used to determine the starting dose of AZD8931 to be used in the current study:

Preliminary non-validated pharmacokinetic and blinded safety data from Part A of the study indicate that single doses of 2.5 mg, 10 mg, 40 mg, 80 mg, 160 mg and 200 mg were well tolerated. No subject experienced a clinically relevant change in safety parameters such as physical examinations (including ophthalmological assessments), BP, pulse, ECG parameters, urinalysis, faecal occult blood, clinical chemistry or haematological assessments. Asymptomatic corneal epithelial changes, detected by fluorescence staining, were noted in 1/5 healthy volunteers treated at 200 mg in this study. These findings were suggestive of superficial desquamation, and an external ophthalmology expert confirmed that normal environmental factors (eg, swimming in chlorinated water) could result in similar observations. These findings were seen on day 5 only and began resolving within a few hours of being noticed, complete resolution being documented 3 days later. The external ophthalmologist providing corneal evaluation expertise to the AZD8931 clinical studies and involved in the ophthalmic clinical evaluations has deemed these findings as highly unlikely to be a drug-related event.

The non-validated PK results showed that AZD8931 is orally bioavailable over the dose range 2.5 mg to 200 mg. Absorption was moderately rapid with time to reach maximum plasma concentration (t_{max}) occurring in most subjects at 1.5 or 2 hours after the dose (range 0.5 to 4 hours). After reaching the maximum plasma concentration (C_{max}), plasma concentrations declined biphasically. A terminal phase became apparent from about 24 hours after the dose,

when the plasma concentrations had fallen to around 6% of the peak values. The mean terminal elimination half-life ($t_{1/2}$) across the dose range was 12.1 hours (range 7.6 to 16.6 hours).

Based on the above data, it was determined that twice-daily administration should be employed in the current study to avoid excessive fluctuations between steady state (ss) C_{max} ($C_{ss_{max}}$) and minimum plasma concentration ($C_{ss_{min}}$). It is predicted that twice-daily dosing will lead to accumulation of study drug at about 30%, with a 5-fold fluctuation between $C_{ss_{min}}$ and $C_{ss_{max}}$.

1.2 Rationale

The key aim of this study is to generate data that may support the opportunity for AZD8931 in the treatment of patients with solid malignancies.

1.2.1 Rationale for safety and pharmacokinetics

AZD8931 is a new investigational medicinal product intended for the treatment of solid malignancies. Non-clinical studies have demonstrated the potential for AZD8931 to produce various toxicities in addition to its anti-cancer effect, possibly secondary to its pharmacological action (see Section 1.1.1). It is therefore imperative to determine the safety and tolerability of AZD8931 in the intended patient population before further studies of its potential efficacy can be done. It is also necessary to determine the PK profile of AZD8931 in this patient population to assess whether the intended dosing schedule will provide adequate exposure to the investigational product.

This study is therefore intended to assess the safety, tolerability, MTD and PK of AZD8931 in patients with advanced solid malignancies.

1.2.2 Rationale for planned biomarker research

As an exploratory objective, it is planned to investigate the correlation between cell death (pro-apoptosis) biomarkers and AZD8931 therapy. This may provide preliminary evidence that AZD8931 induces apoptosis and tumour necrosis in EGFR- and Erb-driven tumours.

1.2.3 Rationale for pharmacogenetic research

As an exploratory objective, it is planned to take blood samples for future pharmacogenetic analysis, with the intention to determine any potential ability to identify individuals who may respond optimally to AZD8931 or a specific dose of AZD8931, or to identify factors that may affect the absorption, distribution, metabolism or excretion or tolerability of AZD8931 or its comparators.

1.2.4 Rationale for efficacy assessments

As an exploratory objective, the anti-tumour activity of AZD8931 will be investigated. Patients who complete the DLT evaluation period and who do not meet any discontinuation criteria are permitted to continue on the study. Efficacy will be assessed by means of Response Evaluation Criteria In Solid Tumours (RECIST) evaluations, and by changes in

tumour length, every 6 weeks (relative to the first day of AZD8931 dosing). Results will be preliminary only, but will be used to aid design of future studies.

This study will be conducted in compliance with the protocol, International Conference on Harmonisation (ICH) Good Clinical Practice (GCP) and applicable regulatory requirements.

2. STUDY OBJECTIVES

2.1 Primary objective

The primary objective of this study is to explore the safety and tolerability of multiple ascending doses (MAD) of AZD8931 in patients with advanced solid malignancies, by evaluation of AEs, laboratory findings, physical examinations, vital signs, cardiac monitoring, and ophthalmological assessments.

2.2 Secondary objectives

The secondary objectives of this study are:

1. To identify the MTD of AZD8931 following repeated twice daily administration, by assessment of DLT
2. To explore the PK of single doses of AZD8931 in patients with advanced solid malignancies
3. To explore the PK of multiple doses of AZD8931 in patients with advanced solid malignancies

Exploratory objectives of this study are:

4. To measure cell death biomarkers from blood samples to examine the relationship to treatment with AZD8931 (optional)
5. To obtain a blood sample for host pharmacogenetics for deoxyribonucleic acid (DNA) extraction and archiving (optional)
6. To obtain preliminary assessments of the efficacy of AZD8931 (including RECIST criteria and change in tumour length).

3. STUDY PLAN AND PROCEDURES

3.1 Overall study design

This Clinical Study Protocol has been subjected to a peer review according to AstraZeneca () standard procedures.

3.1.1 Overall design

This study is an open-label, MAD, phase 1 study to explore the safety and tolerability of AZD8931.

Adult patients with advanced solid malignancies will be eligible for enrolment into this study. Written informed consent for participation in the study is required from the patient before any study specific procedures are conducted.

A minimum of 3 and a maximum of 6 eligible patients will be dosed initially. At the discretion of SMC or, if 1 patient within a dose cohort experiences a DLT, additional patients can be enrolled to ensure the cohort includes a maximum of 6 evaluable patients. Dose escalation may occur if the SMC declares the dose level as tolerable (as detailed in Section 3.1.2 for dose escalation and recruitment procedures). The dose will initially be escalated by dose doubling, up to a level where the SMC decide that smaller escalation steps are warranted. Based on emerging data, including PK and/or safety data and/or pre-clinical data, the SMC can consider alternative schedules, including once-daily dosing of AZD8931, in consultation with AstraZeneca and . There will be adequate time between dose groups to allow review of relevant safety and PK data by the SMC.

Hospitalisation of patients (for safety monitoring or convenience) is at the discretion of the investigator, although the patients should remain at the clinic until completion of the 12 hour post-dose assessments.

Each of the cohorts may remain open until a maximum of 6 patients within the cohort have been defined as evaluable for the dose escalation set (see Table 4), and thereafter further recruitment into that cohort may be closed pending a decision about dose escalation. At the discretion of the SMC, in order to explore any safety concerns in the absence of DLT, each dose level cohort may be expanded to include a maximum of 6 patients who are evaluable for the dose escalation set.

The study design is presented in Figure 2 and the study plan is presented in Table 1.

Patients will have the option to provide a blood sample for genotyping after confirmation of eligibility. Patients who agree to take part in this genetic research will be asked to sign a separate informed consent form to confirm their willingness to have this sample taken. The samples will be stored and may be analysed in future research. See Appendix G for further details on the pharmacogenetics research planned in this study.

AZD8931 tablets will be taken orally. The starting dose level is 40 mg. In each dose group, each patient will receive initial treatment with a single dose of AZD8931, followed by a 4-day observation period then, starting between Day 5 and Day 7, a 21 day repeat dosing (twice daily) treatment period (Days R1 to R21). The 21 days of twice daily dosing with AZD8931 shall constitute a treatment cycle. Hospitalisation of the patients (for safety monitoring or convenience) is at the discretion of the investigator, although the patients should remain at the clinic until completion of the 12 hour post-dose assessments on Days D1 and R14. Patients

should continue treatment after day R21 if, in the investigator's opinion, the patient is receiving or may receive some benefit from therapy, is free from intolerable toxicity and has not met a discontinuation criterion (see Section 3.3.5.1).

Up to approximately 30 evaluable patients with advanced solid malignancies will be included, in approximately 5 dose groups of 3 to 6 evaluable patients, recruited from approximately 4 to 6 centres in Russia and Germany during a recruitment period of approximately 6 months. It is planned to recruit between 5 and 8 evaluable patients at each centre.

AZD8931 dose escalation decisions will be based on a minimum of 3 and a maximum of 6 evaluable patients per dose cohort (for further information see Table 4, dose escalation evaluable set).

3.1.2 Criteria to conduct dose escalation

The DLT evaluation period starts from the first administration of AZD8931 and continues until the completion of all assessments prior to cycle 2. For patients who continue beyond cycle 1, the DLT evaluation period ends following the completion of pre-dose assessments on the first day of cycle 2 (ie R1 cycle 2). For those patients who do not proceed beyond cycle 1 the DLT evaluation period ends following the completion of all assessments on the last day of cycle 1. Following cycle 1, subsequent treatment cycles are continuous. Dose reductions are not permitted during the DLT evaluation period, except following a DLT. If dosing of AZD8931 needs to be interrupted due to intolerable toxicities, then the DLT evaluation period may extend by the appropriate duration. Dose omissions for any other reason must not extend the DLT evaluation period. Evaluability of such patients will depend on meeting the description of analysis sets as described in Table 4 (Section 6.4.3). The cohorts may remain open until a maximum of 6 patients within the cohort have been defined as evaluable and thereafter further recruitment into that cohort will be closed pending a decision from the SMC.

Prior to each dose escalation, the SMC (see Section 6.6) will meet to review the available safety, tolerability (including AEs, laboratory assessments, ophthalmic assessments, physical examinations, vital signs, cardiac monitoring parameters) and PK data. The dose escalation decision will be documented and the minutes will be distributed to each site.

[figure not shown]
Throughout the study, dose escalation decisions will be based on a minimum of 3 and a maximum of 6 evaluable patients per dose cohort (see 'dose escalation evaluable set' described in Table 4). If a patient has received less than 80% of the defined dose and this is due to toxicity, a discussion will take place between AstraZeneca and the investigator to determine if this is a DLT. Replacement patients will enrol until the minimum required number of evaluable patients is available for assessments – see Section 3.4.4 for information on replacement of patients. Reasons for patient withdrawal will be given due consideration when enrolling replacement patients.

The SMC will review the data from each of the patients who completed the DLT evaluation period and decide if dose escalation is appropriate according to the following criteria:

- If DLT is observed in ≥ 2 patients within the DLT evaluation period then this dose will be declared as non-tolerated and dose escalation will stop. A lower dose may be investigated at the discretion of the SMC (Section 6.6).
- If during the DLT evaluation period a DLT is observed in 1 patient within a dose level cohort consisting of less than 6 evaluable patients, additional patients will be recruited, to maintain a maximum of 6 evaluable patients in the cohort
- If during the DLT evaluation period there are no DLTs observed within a dose level cohort, containing 3 to 6 patients evaluable for the presence of DLT, then the dose will be defined as tolerable and dose escalation will continue with an incremented increase in a new group of at 3-6 patients.

Figure 1 summarises the rules to be applied.

Figure 1 Phase I dose escalation decision tree

Footnotes:

Patients in the above schematic refer to evaluable patients (dose escalation set).

^a At the discretion of the SMC, in order to explore any safety concerns in the absence of DLT, each dose level cohort may be expanded to include a maximum of 6 patients who are evaluable for the dose escalation set.

Abbreviations: DLT: dose-limiting toxicity, MTD: maximum tolerated dose

The dose will initially be escalated by dose doubling, up to a level where the SMC decide that smaller escalation steps are warranted, based on PK and/or safety data. If the exposure in patients is more than 10% to 15% greater than predicted based on data obtained in healthy subjects, the dose escalation may proceed in a more conservative manner. The SMC will determine the dose escalation based on the above criteria at the end of each dose group.

Based on emerging data, including PK and/or safety data and/or pre-clinical data, the SMC can consider alternative schedules, including once-daily dosing of AZD8931, in consultation with AstraZeneca and

When a non-tolerated dose is defined, dose escalation will be stopped and the MTD will be confirmed (see Section 3.1.4).

Following each dose decision, the patients already receiving study medication may remain on treatment at their original dose if, in the opinion of the investigator, the patient is receiving some benefit from therapy, is free from intolerable toxicity and does not meet one of the discontinuation criterion listed in Section 3.3.5.1.

Intra-patient dose escalation is not permitted.

If the patient experiences an AZD8931-related toxicity, their dose may be withheld or reduced (see Section 3.4.3).

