3.1.6 Study flow chart and study plan

Figure 2 Study flow chart

3 to 6 patients	Single dose	4-day observation period	Twice daily dosing for 21 days	Data collection /review	SMC review	Single dose	4-day observation period	Twice daily dosing for 21 days...
Day	D1		D5 to 7			(1)		
Repeat dosing day			R1.....R21					

(1) New dose group (increased dose, same dose, decreased dose) depending on result of SMC meeting to discuss previous dose cohort of 3 to 6 evaluable patients (see Section 6.6).

Abbreviations: SMC: Safety Monitoring Committee. Shading: AZD8931 treatment.

Table 1 Study plan

Assessments	Screening	DLT Evaluation Period ^a									Premature discontinuation	Continuation beyond R21 ^a	Post-study follow-up
		Single dose											
Day (h = hours)	D-21 to D0	D1	D2 (24 h)	D3 (48 h)	D4 (72 h)	D5 to D7						Every 3 weeks	7 days after last dose
Repeat dosing (R) day (d=day)						R1	R3	R7 ±1d	R14 ±1d	R21 ±1d	≤2d	±3d	±1d
Informed consent (main study, genetics [optional], proapoptotic biomarkers [optional])	x												
Inclusion/exclusion criteria	x												
Tumour TNM stage at diagnosis and at study entry (and ErbB2 status, if available)	x												
Tumour assessment (RECIST)	x ^b										x ^c	x ^d	
Chest X-ray	x												
Demographics	x												
Medical/surgical history	x												
Previous anticancer therapy, including surgery	x												
Urine pregnancy test	x												
Administer AZD8931		Single dose ^e				Twice daily for 21 days ^e						Twice daily ^e	
Physical examination	x										x		x
Dermatological examinations ^f	x									x	x		x ^g

Table 1 Study plan

Assessments	Screening	DLT Evaluation Period ^a									Premature discontinuation	Continuation beyond R21 ^a	Post-study follow-up
		Single dose											
Day (h = hours)	D-21 to D0	D1	D2 (24 h)	D3 (48 h)	D4 (72 h)	D5 to D7						Every 3 weeks	7 days after last dose
Repeat dosing (R) day (d=day)						R1	R3	R7 ±1d	R14 ±1d	R21 ±1d	≤2d	±3d	±1d
Ophthalmological assessments	x									x	x	x ^h	x ^g
Echocardiography	x									x	x	x ⁱ	x ^g
12-lead Electrocardiogram ^j	x	x ^k	x	x	x	x	x ^l	x ^l	x ^k	x	x	x	x
Vital signs (heart rate, blood pressure)	x	x ^k	x	x	x	x	x ^l	x ^l	x ^k	x	x	x	x
Blood sample for AZD8931 pharmacokinetic (PK) analysis		x ^k	x	x	x		x ^l	x ^l	x ^k				
Blood sample for clinical chemistry, haematology, coagulation parameters	x	x ^{l,m}	x	x	x	x ^l	x ^l	x ^l	x ^{l,m}	x ^l	x	x	x

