4.1.2 Treatment period medical examinations

Refer to [Table 1](#) for details of examinations to be performed during the treatment period. Ophthalmological and dermatological assessments are detailed in Sections [4.4.4](#) and [4.4.5](#), respectively.

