4.1.4 Post-study medical examination

A post-study medical examination will be conducted approximately 7 days after last dose of AZD8931, as specified in [Table 1](#). Patients will be asked to contact their doctor (general practitioner) should they develop any eye symptoms in the 3 months after their post-study medical examination.

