4.7.1.2 Recording of adverse events

Time period for collection of AE/SAEs

Non-serious AEs and SAEs will be collected from the time informed consent is given and throughout the treatment period until 30 days after the last dose of study drug.

Method for detecting AE/SAEs

The method of detecting AE and SAEs in this study will be by:

- Information volunteered by the patient, or carer
- Open-ended and non-leading verbal questioning of the patient at every visit, such as the following: “How are you feeling? Have you had any (other) medical problems since your last visit?”
- Observation by the investigational team, other care providers or relatives

Collection of AE data

All AEs will be recorded on the pCRFs provided. A description of the event, including its date of onset and resolution, whether it constitutes a SAE or not, any action taken (eg, changes to study treatment, other treatment given, follow-up tests) and outcome, should be provided along with the investigator’s assessment of causality (the relationship to the study treatment[s]). AEs will also be graded according to the NCI CTCAE, version 3 ([Appendix E](#)). The maximum CTCAE grade must be recorded on the CRF.

AEs will be coded according to the latest version of Medical Dictionary for Regulatory Activities (MedDRA).

Causality

For an AE to be a suspected drug-related event, there should be at least a reasonable possibility of a causal relationship between the study medicinal product and the AE (see [Appendix B](#) for guidelines on interpretation of causality).

Deaths

All deaths that occur during the study, or within 30 days after the administration of the last dose of study treatment, must be reported as follows:

- Death that is clearly the result of PD should be reported to the study monitor at the next monitoring visit and should be documented in the pCRF but should not be reported as a SAE
- Where death is not due (or not clearly due) to PD under study, the AE causing the death must be reported to the study monitor as a SAE within 24 hours. The report should contain a comment regarding the co-involvement of PD, if appropriate, and should assign main and contributory causes of death
- Deaths with an unknown cause should always be reported as a SAE. A post mortem may be helpful in the assessment of the cause of death, and if performed a copy of the post mortem results should be forwarded to Medical Services within the usual timeframes

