6.4.2 Description of variables in relation to hypotheses

6.4.2.1 Primary variables

The primary objective of the study is to investigate the safety and tolerability of AZD8931. This will be done through review of:

- AEs
- Physical examination results
- Dermatological examinations
- Ophthalmological assessments
- Vital signs (BP and heart rate)
- ECG parameters
- Echocardiographic parameters
- Clinical chemistry, haematology and urinalysis.

No formal hypotheses will be associated with these variables.

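### Table 1 schedules no physical examination from D1 to R21 and no contact after about day 7 post-dose, although the protocol relies on data from both

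*Protocol*

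**What the plan says.** **Physical examination.** Section 2.1 states that the primary objective is to be met "by evaluation of AEs, laboratory findings, physical examinations, vital signs, cardiac monitoring, and ophthalmological assessments". Section 6.4.2.1 lists "Physical examination results" among the primary variables. Under section 3.1.2 the SMC "will meet to review the available safety, tolerability" and PK data before each escalation, and physical examinations are named in that list ("including AEs, laboratory assessments, ophthalmic assessments, physical examinations, vital signs, cardiac monitoring parameters) and PK data").

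In Table 1 (section 3.1.6) the row "Physical examination" is marked at screening, premature discontinuation and post-study follow-up only. Section 4.1.2 sends the reader to Table 1 for "details of examinations to be performed during the treatment period" and adds nothing. Section 4.1.3 asks for at least one clinical assessment per cycle in continuing patients, but ties it to the same schedule.

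**AE window.** Section 4.7.1.2 has AEs and SAEs collected from consent and "throughout the treatment period until 30 days after the last dose of study drug". Active questioning takes place at visits. Section 4.1.4 sets the last one: "A post-study medical examination will be conducted approximately 7 days after last dose of AZD8931". Table 1 gives it a window of ±1 day and shows no later visit or call.

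**The concern.** The protocol relies on two kinds of safety data that its own visit schedule does not fully collect.

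For physical examination, a patient who completes cycle 1 has no scheduled examination after the first dose and before the SMC's decision point. During the DLT period the SMC would by design see this variable only for patients who stopped early, who are not representative of the cohort. Section 5.6 limits the main Clinical Study Report to data up to the end of the DLT evaluation period. For patients who complete cycle 1, the reported period therefore holds a baseline examination and nothing to compare with it.

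For AEs, the stated window is longer than the period in which anyone is scheduled to ask. Events in the later part can be recorded, but only if they reach the study by some other route. This matters in the first study of the drug in patients. In rats, radioactivity in the uveal tract fell by less than 25% over 14 days (section 1.1.1.2), and section 4.1.4 asks patients to look out for eye symptoms for 3 months after the post-study examination.

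**Working it through.** The protocol gives no figure to reproduce here. The check reads the schedule against the text and then does one subtraction.

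**Step 1: Table 1 by column.** The table has 13 visit columns: screening, D1, D2, D3, D4, R1, R3, R7, R14, R21, premature discontinuation, continuation and post-study follow-up.

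| Row | Columns marked |
|---|---|
| 12-lead ECG | all 13 |
| Adverse events | all 13 |
| Dermatology | screening, R21, premature discontinuation, post-study |
| Ophthalmology | screening, R21, premature discontinuation, continuation, post-study |
| Echocardiography | screening, R21, premature discontinuation, continuation, post-study |
| Physical examination | screening, premature discontinuation, post-study |

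Each of these rows splits into exactly 13 cells, and dermatology, ophthalmology and echocardiography all fall on R21. The blank R21 cell for physical examination is therefore unlikely to be a fault of text extraction. Physical examination is marked on 0 of the 9 scheduled days from D1 to R21, and not in continuation.

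**Step 2: where the remaining examinations fall.** Section 3.1.2 ends the DLT evaluation period on the last day of cycle 1 for patients who stop there, and after the pre-dose assessments on R1 of cycle 2 for those who continue.

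- Premature discontinuation: examined within 2 days, so the result can reach the SMC.
- Stops at R21: next examined about 7 days after the last dose, after the DLT period has ended.
- Continues: no scheduled examination until the patient comes off treatment.

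**Step 3: AE window.** Days without scheduled contact = 30 − day of last visit.

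| Last visit (day after last dose) | Days without scheduled contact | Share of 30 days |
|---|---|---|
| 6 | 30 − 6 = 24 | 24/30 = 80% |
| 7 | 30 − 7 = 23 | 23/30 = 77% |
| 8 | 30 − 8 = 22 | 22/30 = 73% |

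These percentages are shares of days, not of events.

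**The case against.** The best defence is that neither gap disables the plan.

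- **The SMC text is qualified.** It reviews what is available, so section 3.1.2 does not promise an examination at R21 for every patient. It meets after the last patient in a cohort has finished the DLT period, so a patient who stopped at R21 earlier may already have had the post-study examination. This stands and makes the mismatch softer than a strict contradiction.
- **Escalation turns on DLTs.** No DLT criterion in section 3.1.5 requires a scheduled general examination. The SMC has on-treatment AEs, vital signs, ECG and laboratory results, full eye and skin examinations and echocardiography at R21, brief eye checks at all visits (section 4.4.5) and symptom-directed skin checks (section 4.4.4). This also stands. None of these is the multi-system examination of section 4.1.1, but no escalation decision is shown to change.
- **AEs have other routes in.** Section 4.7.1.2 also accepts reports from patients, carers, relatives and other care providers, requires proactive follow-up after an initial AE report, and requires deaths within 30 days to be reported. This stands: what is missing is scheduled contact.
- **Exposure is short.** With the preliminary mean half-life of 12.1 hours (range 7.6 to 16.6; section 1.1.2), day 7 is 168/12.1 ≈ 14 half-lives after the last dose, or 168/16.6 ≈ 10 at the longest value. Moreover, the rat finding concerns radioactivity, not measured drug, and the dose-limiting eye toxicity in dogs was corneal (section 1.1.1.3). This lowers the expected yield of late contact. It does not explain why the protocol sets a 30-day window and then schedules no enquiry in most of it. The 3-month eye advice directs patients to their general practitioner, and section 4.1.4 states no route from there to the study.

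**Conclusion.** Both mismatches are real and should be reconciled; neither changes a numerical design figure. For patients who complete cycle 1, a variable named in the primary objective has no scheduled post-dose value inside the period that the main report covers. About 23 of the 30 days after the last dose (22 to 24) have no scheduled contact and rest on volunteered reports, observation by others and follow-up of known events. The conclusion assumes that Table 1 was read correctly and that no other study document schedules these contacts.

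A reader might infer more than this, and three stronger readings fail:

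- That physical examination is observed only in patients who discontinue. It is scheduled for all patients at screening and after the last dose; the restriction to premature discontinuation applies within the DLT period only.
- That there is no contact for AEs after day 7. Only scheduled contact is absent.
- That 77% of late AEs would be missed. The figure is a share of days. Under-ascertainment is possible, but the documents give no basis for its size.

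**What to change.** Reconcile Table 1 with sections 2.1, 3.1.2, 6.4.2.1 and 4.7.1.2 by two additions:

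1. A physical examination mark at R21, a visit that already has eye, skin, echocardiography, ECG and laboratory assessments.
2. A telephone AE check at day 30 after the last dose.

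Keep the 30-day AE window. Shortening it to 7 days would also remove the inconsistency, but it would discard AEs and SAEs reported between day 8 and day 30 and would sit badly with the reporting of deaths within 30 days in section 4.7.1.2.

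The cost is a few minutes at an existing visit and one call per patient.
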